#### 4.3. DLT Criteria

DLT events for dose escalation decisions will be assessed to the end of Cycle 1 for each patient in each cohort, except in the case of protracted neutropenia in the absence of active AML, where evaluation of the event must be conducted over 42 days. Ongoing safety events beyond Cycle 1 will be reviewed across all cohorts during the study to help inform dose escalation decisions.

AEs will be graded according to the NCI CTCAE V4.03. The AEs listed below will be considered as DLT unless they are clearly and incontrovertibly attributable to the underlying disease or to an extraneous cause:

- Grade 5 toxicity
- Grade 4 neutropenia lasting  $\geq$ 42 days from the start of the therapy cycle in absence of evidence of active AML (<5% blasts)
- Grade 3 or 4 non-hematologic toxicity, except:
  - Alopecia;
  - Grade 3 fatigue, asthenia, anorexia, fever, or constipation;
  - Grade 3 nausea, vomiting, or diarrhea not requiring tube feeding, TPN, or hospitalization;
  - Infection, bleeding, or other expected direct complications of cytopenias due to active leukemia;
  - Grade 3 or 4 electrolyte imbalances that respond to correction i.e. return to  $\leq$ Grade 2, within 48 hours (h) from correction's onset;
  - Grade 3 increase in aspartate aminotransferase (AST) and/or, alanine aminotransferase (ALT) and/or alkaline phosphatase (ALP) recovering  $\leq$ Grade 2 within 7 days.

Only **clinically significant** abnormalities in laboratory findings, physical examination, vital signs, weight or ECG (see [Section 7.2](#)) will be considered for DLT assessment, according to the protocol definition.

Please refer to [Section 7.7.3](#) for details of how to report DLT events.

#### 4.4. Criteria for Re-treatment and Dose Modification Rules

The following sections describe the requirements for proceeding with treatment with SEL24/MEN1703 from Cycle 2 onwards, and the protocol rules for dose modification due to toxicity.

From Cycle 2 onwards, each patient's liver and renal function tests must return to the values required for entry into the study ([Section 3.1](#)) or better, in order to continue treatment in the next cycle. This requirement may be achieved by following a dose delay as described below.

In the case of SEL24/MEN1703-related non-hematologic toxicity, the dose modification rules to be followed in both parts of the study are presented in Table 10. No more than two dose reductions for toxicity will be permitted before withdrawal of study treatment.

**Table 10: Dose Modification of SEL24/MEN1703 for Non-hematologic Toxicity**

CTCAE Grade	Occurrence of Specified Event	SEL24/MEN1703 Dose Modification
≤Grade 2 (tolerable)	Any	Maintain patient's starting dose if toxicity can be tolerated
Grade 2 intolerable	1 st	Delay treatment by up to 2 weeks; 
 
- If toxicity resolved, re-start at same dose level
 
- If toxicity not resolved, re-start at dose level below*
 

	2 nd	If at patient's starting dose, delay treatment by up to 2 weeks; 
 
- If toxicity resolved, re-start at dose level below*
 
 If at dose level below patient's starting dose; 
 
- Discontinue permanently
 

	3 rd	Discontinue permanently
Grade 3	1 st	Delay treatment by up to 2 weeks; 
 
- If toxicity resolved, re-start at dose level below*/**
 
- If toxicity not resolved, permanently discontinue**
 

	2 nd	Discontinue permanently**
Grade 4	Any	Discontinue permanently**

\*dose reductions lower than 25 mg are not possible

\*\*patients with Grade 3 or 4 electrolyte imbalances that respond to correction i.e. return to ≤Grade 2, within 48 h from correction's onset may re-start at the same dose level; if the event occurs a 2nd time, the patient must re-start at the dose level below; if the event occurs a 3rd time, they must be permanently discontinued.

After Cycle 1, in case of hematologic toxicity the bone marrow status will guide the initiation of the next cycle according to Table 11 (NOTE: bone marrow examination may not be performed in case peripheral labs indicate persistence of disease):

**Table 11: Dose Modification of SEL24/MEN1703 for Hematologic Toxicity**

Bone marrow status	SEL24/MEN1703 Dose Modification
No remission	Next cycle may commence immediately
Remission	Next cycle may commence once peripheral count recovery has been achieved
Hypocellular (<5% cellularity without evidence of leukemia blasts)	
Next cycle may not commence until peripheral counts recover
 
 
Once peripheral counts recover, start SEL24/MEN1703 at same dose level if recovery by Day 42
 
If peripheral count recovery occurs beyond Day 42, then a one dose level reduction of SEL24/MEN1703 for subsequent treatment cycles should be implemented, once peripheral counts recover
 

Achieved CR or CRi, with G3 or 4 hematologic toxicity (e.g. febrile neutropenia)	Consider one dose level reduction of SEL24/MEN1703 for subsequent treatment cycles, once peripheral counts recover

The Investigator may determine the resumption of next treatment cycle based on clinical judgement. Deviations from the above guidelines are permitted to ensure safety and serve the best interest of the patient according to the assessment and judgement of the Investigator. The reason for deviating from the guidelines should be documented in source documents.

Dosing may be withheld in the presence of non-drug related Grade 3 or 4 adverse event if the Investigator feels that it is unsafe to continue the administration of SEL24/MEN1703.

In general, a patient who requires more than two dose reductions will be removed from the study unless, in the opinion of the investigator, the patient is experiencing a clinical benefit defined as achieving CR, CRi, CRh, PR or stable disease without unacceptable toxicities. In such cases, a decision regarding the continuation of treatment with SEL24/MEN1703 and further dose reductions will be made on an individual basis in consultation with the medical monitor and the justification will be recorded in the source documents. All dose modifications will be captured in the eCRF.

Patients will be monitored for compliance throughout the study and may be withdrawn if considered to be non-compliant (see [Section 3.4](#)). In Part 1 (from Cycle 2 onwards only) and in Part 2, an extended treatment delay e.g. of up to 14 days, may be permitted on one occasion, either before commencing a new treatment cycle or during a treatment cycle, for reasons unrelated to SEL24/MEN1703 toxicity where the Investigator considers the treatment delay to be exceptional and that it remains in the patient's best interests to continue with SEL24/MEN1703.

#### 4.5. Intra-patient Dose Escalation

In Part 1, intra-patient dose escalation will be permitted per patient at the discretion of the Investigator, and in consultation with the DMC. The selected dose for the escalation step must

have been confirmed as well-tolerated (i.e. patients must have been evaluated to the end of Cycle 1, and the dose level does not exceed the MTD). The patients must also have completed 2 or more cycles of treatment at their starting dose without experiencing any DLT or its equivalent. Intra-patient Dose Escalation is not permitted in Part 2.

## 5. STUDY SCHEDULE

The study consists of a Screening period, Treatment cycles, a Final Study Visit, plus Follow-up Assessments. Informed consent must be obtained using the current version of the Patient Information Sheet (PIS)/Informed Consent Form (ICF) prior to commencing Screening. Patients will attend the clinic for Screening assessments up to a maximum of 28 days before receiving the first dose of SEL24/MEN1703. Due to the nature of the disease being studied, it is likely that Screening assessments will in practice be carried out over a shorter time period. The Final Study Visit assessments will occur up to 30 days after the patient has discontinued SEL24/MEN1703 study treatment. A final AE and concomitant medication review must take place 30 days after the last dose of SEL24/MEN1703. Follow up assessments will be conducted, wherever possible, every 3 months after the Final Study Visit regardless of initiation of additional treatments for up to 1 year (or until End of Study, whichever occurs first).

The following sections provide a detailed listing of study assessments by visit. A summary of this information is also provided in Schedule of the Study Assessment (Table 5).

Patients will be required to visit the study sites for each study visit. Permitted tolerance windows for specific study visits and assessments may apply and are described in the Schedule of Study Assessment (Table 5) and in its footnotes. Where these are applied, the same tolerance windows may also be used for the entire study visit and all other assessments scheduled to be conducted at that visit.

### 5.1. Schedule of Study Assessments

Each section below provides a summary of study assessments described by visit.

Please also refer to the Schedule of Study Assessments (Table 5) and associated footnotes.

Informed Consent must be obtained using the current version of the PIS/ICF prior to commencing Screening. On dosing days, assessments should be performed prior to SEL24/MEN1703 dosing unless specified otherwise. Additional assessments may be conducted as clinically indicated. Where possible, patients will be followed up every 3 months for up to 1 year from their Final Study Visit regardless of initiation of additional treatments to check for disease progression and survival status. This assessment may be made by telephone interview or performed during the patient's routine clinic visits following completion of participation in the study. If the patient is lost to follow-up public databases can also be searched.

The following list of assessments is based on 14 days of SEL24/MEN1703 treatment in 21-day cycles, further details, including possible exceptions for samples to be collected, are reported in the Schedule of Study Assessments (Table 5) and its footnotes.

#### Screening (up to a maximum of 28 days prior to first dose of SEL24/MEN1703)

- ~ Demographics
- ~ Medical history
- ~ Inclusion/exclusion check
- ~ FSH/Pregnancy testing (as appropriate; pregnancy test to be conducted within 7 days of the first SEL24/MEN1703 administration)
- ~ ECOG PS

- ~ Vital signs
- ~ Physical examination
- ~ Clinical chemistry
- ~ Hematology
- ~ Coagulation
- ~ Lipid profile
- ~ Peripheral blasts
- ~ Urinalysis
- ~ ECG
- ~ Echocardiogram (or MUGA scan, if this is preferred standard, local cardiac assessment)
- ~ Bone marrow aspirate/biopsy (local bone marrow differential to be performed)
- ~ Genetic profile of AML cells (bone marrow)  
Note: An aliquot of bone marrow aspirates/biopsy will be used
- ~ PD biomarkers (blood)
- ~ CYP2D6 phenotyping (blood)
- ~ CD25 expression (blood)  
Note: An aliquot of blood taken for PD biomarker will be used
- ~ Mutational status
- ~ AML Karyotypic analysis
- ~ Transfusion status
- ~ Concomitant medication

#### Cycle 1, Day 1

- ~ Vital signs
- ~ FSH/Pregnancy testing
- ~ Physical examination
- ~ Clinical chemistry
- ~ Hematology
- ~ Coagulation
- ~ Lipid profile
- ~ Peripheral blasts
- ~ Urinalysis
- ~ ECG (pre-dose and 4-6 h post dose)
- ~ PD biomarkers (blood; pre-dose, 2-6h post dose)
- ~ Adverse events
- ~ Transfusion status
- ~ Concomitant medication
- ~ PK profile sampling (blood; pre-dose, 0.5, 1, 2, 4, 6, 8, 10-14 h post dose)
- ~ PK (urine; Part 1 only)

#### Cycle 1, Day 2

- ~ Clinical chemistry
- ~ Hematology

- ~ Coagulation
- ~ Adverse events
- ~ Transfusion status
- ~ Concomitant medication
- ~ PK sampling (blood; 24 h post C1 D1 dose/C1 D2 pre-dose)
- ~ PK (urine; collect to immediately before D2 dose, Part 1 only)

#### Cycle 1, Days 3 and 4

- ~ Clinical chemistry
- ~ Hematology
- ~ Coagulation
- ~ Adverse events
- ~ Transfusion status
- ~ Concomitant medication

#### Cycle 1, Day 7

- ~ Clinical chemistry
- ~ Hematology
- ~ Coagulation
- ~ ECG
- ~ Adverse events
- ~ Transfusion status
- ~ Concomitant medication
- ~ PK sampling (blood; 4 h and 8 h post dose)

#### Cycle 1, Day 14

- ~ Clinical chemistry
- ~ Hematology
- ~ Coagulation
- ~ Lipid profile
- ~ Peripheral blasts
- ~ PD biomarkers (blood; 2-6h post dose)
- ~ Adverse events
- ~ Transfusion status
- ~ Concomitant medication
- ~ PK profile sampling (blood; pre-dose, 0.5, 1, 2, 4, 6, 8, 10-14 h post dose)

Note: PD and PK sampling times are relative to last dose in C1.

#### Cycle 1, Day 15

- ~ PK sampling (blood; 22-26 h post C1 D14 dose)

Note: PK sampling times are relative to last dose in C1.

Cycle 1, Day 17

- ~ PK sampling (blood; 70-74 h post C1 D14 dose)

Note: PK sampling time is relative to last dose in C1.

Cycle 1, Day 19

- ~ PK sampling (blood; 118-122 h post C1 D14 dose)

Note: PK sampling time is relative to last dose in C1.

Cycle 2, Day 1

- ~ ECOG PS
- ~ Vital signs
- ~ FSH/Pregnancy testing
- ~ Physical examination
- ~ Clinical chemistry
- ~ Hematology
- ~ Coagulation
- ~ Lipid profile
- ~ Urinalysis
- ~ ECG
- ~ PD biomarkers (blood; pre-dose)
- ~ Adverse events
- ~ Transfusion status
- ~ Concomitant medication
- ~ PK sampling (blood; pre-dose)

Cycle 2, Day 7

- ~ Clinical chemistry
- ~ Hematology
- ~ Coagulation
- ~ Adverse events
- ~ Transfusion status
- ~ Concomitant medication
- ~ PK sampling (blood; 2-6 h post dose)

Cycle 2, Day 14

- ~ Clinical chemistry
- ~ Hematology
- ~ Coagulation
- ~ Lipid profile
- ~ Peripheral blasts

- ~ PD biomarkers (blood; 2-6 h post dose)
- ~ Adverse events
- ~ Transfusion status
- ~ Concomitant medication
- ~ PK sampling (blood; 2-6 h post dose)

#### Cycle 3 onwards, Day 1

- ~ ECOG PS
- ~ Vital signs
- ~ FSH/Pregnancy testing
- ~ Physical examination
- ~ Clinical chemistry
- ~ Hematology
- ~ Coagulation
- ~ Lipid profile
- ~ Urinalysis
- ~ ECG
- ~ Bone marrow aspirate/biopsy (mandatory as soon as peripheral lab results become consistent with an objective response and at Cycle 3; recommended every 2 cycles thereafter)
- ~ Disease evaluation (optional; recommended every 2 cycles)
- ~ Genetic profiling (bone marrow, recommended every 2 cycles)  
Note: An aliquot of bone marrow aspirates/biopsy will be used
- ~ PD biomarkers (blood; pre-dose)
- ~ Adverse events
- ~ Transfusion status
- ~ Concomitant medication
- ~ PK sampling (blood; pre-dose)

#### Cycle 3 onwards, Day 14

- ~ Clinical chemistry
- ~ Hematology
- ~ Peripheral blasts
- ~ PD biomarkers (blood; 2-6 h post dose)
- ~ Adverse events
- ~ Transfusion status
- ~ Concomitant medication
- ~ PK sampling (blood; 2-6 h post dose)

#### Final Study Visit

- ~ ECOG PS
- ~ Vital signs

- ~ FSH/Pregnancy testing (if Final Study Visit is performed after at least 30 days from last study drug administration; otherwise this test shall be postponed when 30 days have elapsed from last study drug administration)
- ~ Physical examination
- ~ Clinical chemistry
- ~ Hematology
- ~ Coagulation
- ~ Lipid profile
- ~ Peripheral blasts
- ~ Urinalysis
- ~ ECG
- ~ Bone marrow aspirate/biopsy (optional; as required)
- ~ Disease evaluation (optional; as required)
- ~ Genetic profiling (bone marrow; optional, as required)  
Note: An aliquot of bone marrow aspirates/biopsy will be used
- ~ Adverse events
- ~ Transfusion status
- ~ Concomitant medication

### Follow-Up

- ~ Follow-up assessments (a visit or a telephone call, as per local practice)

**IMPORTANT NOTE:** in addition to the optional time points above described, bone marrow aspirate/biopsy is mandatory at Screening and as soon as the peripheral lab results become consistent with an objective response.

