**General instructions:**

- Informed Consent must be obtained using the current version of the PIS/ICF prior to commencing Screening.

- On dosing days, assessments should be performed prior to SEL24/MEN1703 dosing unless specified otherwise; tolerance windows for specific assessments are described below.
- (X) denotes an optional sample; please refer to Footnotes.
- X§ denotes a sample not taken at every cycle; please refer to Footnotes.
- Additional assessments may be performed as clinically indicated.

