- 7 Bone marrow aspirate/biopsy shall be taken at the following time points: at Screening, either as soon as peripheral lab results become consistent with an objective response or at C3 D1 whichever comes first, at a recommended frequency of every 2 cycles thereafter e.g. C5 D1, C7 D1, etc. (-2 d tolerance) or as clinically indicated, at relapse and FSV. In case of AML relapse following response to SEL24/MEN1703, a bone marrow aspirate/biopsy is highly recommended, whenever possible. Time-points described as (X)§ are recommended every 2 cycles, but not mandatory. Patients may not have the FSV assessment performed where they already have had a bone marrow assessment in the last month or have progressive disease. A bone marrow differential will be performed locally. An aliquot of bone marrow aspirate/biopsy will be centrally stored for future analysis (e.g. minimal residual disease), if any. Please refer to the Lab Manual for full details on bone marrow aspirates/biopsy collection, time-points, processing, storage and shipment.
- 8 Disease evaluation will be performed at every time-point (excluding Screening) where a bone marrow aspirate/biopsy is taken.
- 9 Bone marrow aspirate/biopsy taken during the study will be tested centrally for the genetic profile of AML cells. Please refer to the Lab Manual for full details on sample collection, time-points, processing, storage and shipment.
- 10 Blood sampling for PD biomarker assessments will be taken at Screening, C1 D1 pre-dose, C1 D1 2-6h post-dose, C1 D14 2-6h post-dose, C2 D1 pre-dose, C2 D14 2-6h post-dose, C3 D1 pre-dose, C3 D14 2-6h post-dose. All sample times are approximate and every effort should be made to take the samples as close to the specified time given and, where relevant, contemporaneously with blood sampling for PK assessments. For the C1 D1 and D14 a ±30 min window is allowed. Please refer to the Lab Manual for full details on PD biomarker sample collection, time-points, processing, storage and shipment.

- 11 CYP2D6 phenotyping will be assessed centrally on a blood sample collected at Screening.
- 12 CD25 expression will be assessed centrally on an aliquot of blood sample for PD biomarker assessment taken at Screening.
- 13 Mutational status (including at least FLT3 and IDH mutations) will be assessed locally at Screening.

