### 3.3. Definition of Evaluable Patient and Replacement of Patients

In Part 1 Cycle 1, a patient must have received at least 12 of their 14 doses of SEL24/MEN1703 within the required 14-day treatment period in order to be evaluable. If a patient is withdrawn from the study for reasons other than a DLT-associated event before the end of the first treatment cycle, the patient must be replaced so that the required number of patients in the cohort is evaluable for the dose escalation decision. Patients who withdraw from the study or discontinue treatment after completion of the first treatment cycle will not be replaced.

In Part 2, patients may be replaced if they are not considered evaluable for safety (all patients who received at least a dose of SEL24/MEN1703). Patients in Part 2 may also be replaced if they received one or more administrations of SEL24/MEN1703 without having one post-treatment bone marrow disease assessment.

In this latter event, patients may be replaced only if the hematology assessments performed on peripheral blood shall not indicate a clear disease progression.

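### The Cycle 3 Day 1 marrow has conflicting statuses in the protocol, and the SAP does not say how a patient with no post-treatment marrow counts in ORR.

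*Protocol*

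**What the plan says.** **On whether the marrow is required**

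- Protocol 5.1, list for Cycle 3 onwards Day 1: the marrow is "mandatory as soon as peripheral lab results become consistent with an objective response and at Cycle 3; recommended every 2 cycles thereafter". The same list gives disease evaluation as optional.
- Protocol Table 5, footnote 7, opening sentence: after Screening the marrow is due "either as soon as peripheral lab results become consistent with an objective response or at C3 D1 whichever comes first". A recommended two-cycle interval follows, with Cycle 5 and Cycle 7 Day 1 as examples.
- The same footnote, later: time points carrying the bracketed-X symbol with the section sign "are recommended every 2 cycles, but not mandatory". Table 5 puts that symbol on the Cycle 3 onwards marrow. The general instructions define a bracketed X as optional and refer the reader to the footnotes.
- Protocol 5.1, important note after the Follow-Up list: "bone marrow aspirate/biopsy is mandatory at Screening and as soon as the peripheral lab results become consistent with an objective response", in addition to optional time points. Section 5.3.10 says the same and calls the schedule's time points optional.
- Footnote 8 ties a disease evaluation to every marrow after Screening.

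SAP 5.3 repeats the table and footnotes unchanged.

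**On how patients are counted**

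- ORR is the proportion with CR, CRi, CRh or MLFS (SAP 5.4.2). Each needs marrow blasts below 5% (Protocol Appendix D).
- Anti-leukemic activity is analysed on the safety and efficacy populations, with a measured-only subgroup used alongside (SAP 7.3).
- Categorical variables are reported as non-missing observations with percentages (SAP 11.2). An observed-cases approach covers all analyses (SAP 11.3).
- The best-response list in SAP 12.1 runs from CR without MRD to PD and has no not-evaluable category.
- Part 2 patients may be replaced if they "received one or more administrations of SEL24/MEN1703 without having one post-treatment bone marrow disease assessment", unless blood clearly shows progression (Protocol 3.3).
- Three all-comers were replaced and 23 were treated (SAP 8).

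**The concern.** Two sites could treat the same patient differently at Cycle 3 Day 1 and each point to current protocol text. Under 5.3.10, the only compulsory marrow after Screening is the one prompted by favourable blood results. A patient without that prompt could then go unsampled.

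No ORR component can be assigned without a marrow, so an unsampled patient has no known response status. The SAP gives no rule for such a patient. Its general rules on missing data, read literally, leave the patient out of the percentage. ORR could then vary with site practice and with the programmer's choice of denominator, as well as with the drug's activity.

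**Working it through.** **1. The passages side by side.** Status of the Cycle 3 Day 1 marrow for a patient still on study:

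| Source | Not yet sampled | Already sampled on a blood-count trigger |
|---|---|---|
| Protocol 5.1, Cycle 3 list | required | required |
| Footnote 7, opening sentence | required | not required |
| Footnote 7, symbol sentence, with Table 5 and its legend | not required | not required |
| Protocol 5.3.10 | not required | not required |
| Protocol 5.1, note | not required, if Cycle 3 is among its optional points | same |

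The last row is arguable, because the list above that note labels the Cycle 3 marrow mandatory. The other four rows still give three different rules. Disease evaluation has its own conflict: optional in the 5.1 list, but attached to every post-screening marrow by footnote 8.

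**2. No plan figure to reproduce.** The documents give no target ORR and no expected share of patients assessed. SAP 8 says that no formal sample size calculation applies.

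**3. Effect of the denominator.** Let N be treated patients, r detected responders and m patients with no post-treatment marrow. ORR is r/N on all treated and r/(N − m) on assessed patients. N = 20 is the approximate planned IDH cohort (Protocol 4.2); r = 4 and the values of m are assumptions. Intervals are exact 95%.

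| m | Calculation | ORR (95% CI) |
|---|---|---|
| any, all treated | 4/20 | 20.0% (5.7 to 43.7) |
| 3, assessed only | 4/17 | 23.5% (6.8 to 49.9) |
| 6, assessed only | 4/14 | 28.6% (8.4 to 58.1) |
| 9, assessed only | 4/11 | 36.4% (10.9 to 69.2) |

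For the all-comers, if all 3 replaced patients are among the 23 treated and all lacked a marrow, 4 assumed responders give 4/23 = 17.4% against 4/20 = 20.0%. SAP 8 does not say how the 3 split between its two replacement grounds.

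**4. Direction of bias.** Let p be the true ORR, c the share of responders whose blood counts trigger a marrow, and q the chance of a marrow without a trigger. Assume that non-responders never trigger.

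- Expected ORR on all treated: p[c + (1 − c)q].
- Expected ORR on assessed patients: p[c + (1 − c)q] / [pc + (1 − pc)q].

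With p = 0.20 and q = 0.5:

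- c = 0.5: 0.20 × 0.75 = 15.0% on all treated; 0.15/0.55 = 27.3% on assessed.
- c = 0.75: 0.20 × 0.875 = 17.5% on all treated; 0.175/0.575 = 30.4% on assessed.

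With q = 1, both equal 20%. For p from 10% to 30%, c from 0.5 to 0.75 and q = 0.5, the range is 7.5% to 26.3% on all treated (below the true value in each case) and 14.3% to 42.9% on assessed patients (above it in each case).

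**The case against.** The strongest reply is that the two places that name Cycle 3 as a due date agree where it matters: the 5.1 list and footnote 7's opening sentence both give every patient still on study a marrow by Cycle 3 Day 1. The symbol sentence can be read as covering only Cycle 5 and later, and the table legend defers to the footnotes. This narrows the conflict but does not remove it. Table 5 puts the symbol on Cycle 3 onwards without exception, and 5.3.10 calls the schedule's time points optional.

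A reader might infer that ORR rests on selective assessment. The documents do not support that. Two provisions require the marrow, so selective sampling is a risk of the conflict and not the stated plan.

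A reader might also infer that an MLFS, which needs no count recovery, would never be sampled. That goes too far. Clearance of peripheral blasts could count as consistent with response. Protocol 4.4 and Table 11 also use marrow status to guide the next cycle in hematologic toxicity, with an exemption only when blood shows persistent disease.

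A third inference is that replaced patients leave the analysis. They do not: anyone dosed stays in the safety population, and SAP 8 counts 23 treated. Neither main population requires a post-treatment marrow. What remains open is narrower. Belonging to a population does not settle whether a patient with no response value enters the percentage, and SAP 11.2 and 11.3 point towards leaving that patient out.

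Some patients without a marrow could still be classed as PD from blood under Appendix D, so the number at risk of dropping out may be small.

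**Conclusion.** The point holds as a wording conflict combined with a missing SAP rule. The status of the Cycle 3 Day 1 marrow and its disease evaluation is inconsistent in the current text, and the SAP carries the inconsistency over. Patients left without a post-treatment marrow could drop out of the ORR denominator, even in the safety population.

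With 4 responders of 20, moving to an assessed-only denominator adds 3.5 points if 3 patients are unassessed (23.5 − 20.0) and 8.6 points if 6 are (28.6 − 20.0). On all treated patients, each missed response costs 1/20 = 5 points. The responder counts, numbers unassessed and trigger probabilities are assumptions. The documents show that missing marrows were foreseen, but not how many occurred. No net direction of bias can be claimed until the denominator is fixed.

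ORR is a secondary, descriptive endpoint with no hypothesis test, and the intervals at this sample size are far wider than these shifts. The matter is worth correcting because the remedy is cheap. It does not undermine the trial's primary safety objective.

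**What to change.** - Reconcile Protocol Table 5, footnotes 7 and 8, section 5.1 (visit list and note), section 5.3.10 and the copy in SAP 5.3 to one stated status for the Cycle 3 Day 1 marrow and for disease evaluation. Which status applies is for the sponsor to decide.
- In SAP 12.1, compute ORR on all treated patients, including replaced ones, and count those without a post-baseline marrow as non-responders. State that this overrides the observed-cases rule for ORR.
- Add a not-evaluable category to the best-response list, and report how many patients had no post-treatment marrow.

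The SAP changes are needed whichever status is chosen. Cycle 3 Day 1 is nominally Day 43 (2 × 21 + 1), while the efficacy population requires only one completed 21-day cycle with at least 75% of the drug taken. A patient can therefore qualify and stop before that marrow is due.

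The cost is aligned wording, one SAP rule, one extra category and one extra count. The SAP rule needs no new procedure or data. The downside is that ORR may read slightly lower.
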